4.1 Patient Registration

Patients will be centrally registered with the Weill Cornell Medicine (WCM), Division of Hematology and Medical Oncology, Joint Clinical Trials Office. To register a patient, email the following documents to your assigned registration contact:

- WCM Patient registration form
- First and last page of the fully executed informed consent form, plus additional pages if checkboxes for correlative studies are required.
- Fully executed HIPAA research authorization form (if separate from the consent document)
- Eligibility checklist signed and dated by investigator and research nurse
- Documentation of any eligibility waivers granted
- Redacted source documentation to verify eligibility

Central registration documents should be scanned/mailed Monday to Friday from 9:00 AM to 4:00 PM EST to study investigators and [contact], along with all other assigned registration contacts for this study. Central registration information is reviewed and entered into the REDCap database by the Coordinating Center. Patients will be assigned a sequence number for the protocol. The registering institution will then be emailed a copy of the sequence number as confirmation of a completed registration. Subjects should NOT receive any study medication prior to receipt of registration confirmation. Note that attachments larger than 4.5 MB are not accepted, so larger attachments should be split into more than one email.

Registration of patients cannot occur until the Coordinating Center has received proper documentation from the registering institution of IRB approval, including a copy of the current approval letter, stamped consent and signed FDA Form 1572, along with other required regulatory documents. These documents will be requested at site activation and may be scanned/mailed to the Coordinating Center.

5. Study Procedures

5.1 Schedule of Evaluations

Table 1. Schedule of trial events

Schedule of Assessments				Year 1										
Study Procedure	Screening	C-1	C-1	Cycle 1				C2 D1	C3 D1	C4 D1	C5 D1	C6 D1	C7 D1	C10 D1
		D1	D15	Day 1	Day 2	Day 8	Day 15							
Informed Consent	X													
Inclusion/Exclusion	X													
ECOG	X	X	X	X				X	X	X	X	X	X	X
Demographics	X													
Medical History	X	X	X	X	X	X	X	X	X	X	X	X	X	X
Physical Exam	X	X	X	X	X			X	X	X	X	X	X	X
Vital Signs	X	X	X	X	X	X	X	X	X	X	X	X	X	X
Height	X													
Weight	X	X	X	X				X	X	X	X	X	X	X
EKG	X													
Bone Marrow Biopsy	X													
Bone Marrow Aspirate	X													
CBC with diff	X	X	X	X	X	X	X	X	X	X	X	X	X	X
Serum Chemistry (CMP) ^a	X	X	X	X	X	X	X	X	X	X	X	X	X	X
HIV Rapid Screen	X													
Hepatitis Antibody Screen ^b	X													
Cytomegalovirus (CMV) PCR	X										X			X
B-HCG ^c (FCBP only)	X													
Circulating DNA (research)		X		X				X						X
Clonal Evolution Analysis (research)		X		X				X						X
Ublituximab Infusion			X	X	X	X	X	X	X	X	X	X	X	
Umbralisib Dispensation		X	X	X				X	X	X	X	X	X	X
Adverse Event Monitoring ^d	At each timepoint AEs will be collected													
Radiologic Evaluation ^e	X							X						X

Schedule of Assessments	Year 2				Year 3+	EOT	Follow-up*
Study Procedure	C13 D1	C16 D1	C19 D1	C22 D1	C25 D1 then Every 3 months	30 days post last dose	Every 3 months
Informed Consent							
Inclusion/Exclusion							
ECOG	X	X	X	X	X	X	X
Demographics							
Medical History	X	X	X	X	X	X	X
Physical Exam	X	X	X	X	X	X	X
Vital Signs	X	X	X	X	X	X	X
Height							
Weight	X	X	X	X	X	X	X
EKG							
Bone Marrow Biopsy							
Bone Marrow Aspirate							
CBC with diff	X	X	X	X	X	X	X
Serum Chemistry (CMP) ^a	X	X	X	X	X	X	X
HIV Rapid Screen							
Hepatitis Antibody Screen ^b							
Cytomegalovirus (CMV) PCR	X	X	X	X	X		
B-HCG ^c (FCBP only)							
Circulating DNA (research)	X		X		X	X	
Clonal Evolution Analysis (research)	X		X		X	X	
Ublituximab Infusion							
Umbralisib Dispensation	X	X	X	X	X		
Adverse Event Monitoring ^d	At each timepoint AEs will be collected						
Radiologic Evaluation ^e	X		X				X (q12mo)

Footnotes:

- * Subjects who discontinue treatment due to toxicity, but have not progressed will continue in study follow-up. Visits should occur q3months after EOT visit or until subsequent non-study drug administration. Patients who discontinue treatment due to progression of disease will enter survival follow-up. Survival follow-up will be documented by phone call every 6 months up to 5 years.
- a. CMP includes a Basic Metabolic panel (Sodium, potassium, chloride, bicarb, blood urea nitrogen, creatinine, calcium, glucose) and a Hepatic function panel (protein total, albumin, globulin, alanine aminotransferase, aspartate aminotransferase, total bilirubin, alkaline phosphatase), Uric acid required only at screening, C-1 D1, C-1 D15, C1 D1, and C1 D2.
- b. Hepatitis antibody screening will consist of Hepatitis A ab, HBsAg, HBcAb, Hepatitis C Ab. If HBcAb is positive, an HBV DNA PCR should be performed.
- c. B-HCG pregnancy testing required only for females of child bearing potential (FCBP). At screening should be tested by serum within 3 days prior to C-1 D1.
- d. Adverse events should be assessed up to 30 days post last dose. For all serious adverse events (SAE), concomitant medications should be assessed and appropriately captured/reported.
- e. CT neck, chest, abdomen, pelvis with contrast. Radiologic evaluation during follow-up should occur every 12 months or as clinically warranted to document disease progression.

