1.2. Secondary Objectives

Secondary Objectives: Secondary objectives to be evaluated in the study will be complete remission rate, duration of response, and safety.

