2.4.5 Ublituximab Clinical Studies Safety/Efficacy

CD20-0703

The first in human trial was initiated in November 2008 CD20-0703. Thirty-three subjects were treated which established the safety and schedule of the drug. Of the 33 subjects 45% completed all infusions. Of the 18 subjects who discontinued 13 did due to lack of efficacy, 2 due to AEs and 1 withdrew consent. A total of 332 adverse events (AEs) were experienced with 170 of them attributable to ublituximab. Of those 170 AEs, 146 occurred during the study infusion period. Drug related grade 3 and 4 events were reported in 63.6% and 27.3%, respectively most commonly related to neutropenia, infusion reactions, and elevated liver enzymes. The most frequent drug-related AEs were infusion related reactions (60.6%), pyrexia (54.5%), neutropenia (45.5%), thrombocytopenia (30.3%), headache (24.2%), chills (21.2%), elevated liver enzymes (18.2%), nausea and asthenia (12.1%).

Twenty three infusion related reactions (IRR) were reported in 20 subjects. Sixteen of the IRRs were Grade 2, and 7 were Grade 3. Sixteen of the 23 IRRs occurred after the first infusion of ublituximab, 3 after the second infusion, and 4 after subsequent infusions. Fifteen drug-related infections were reported in 9 subjects. Ten of the 15 were mild to moderate upper respiratory infections, herpes outbreaks, or anal abscesses. Grade 3 or greater infections were noted in 5 patients in heavily pretreated patients with listeriosis, pulmonary aspergillosis, varicella and staph aureus sepsis.

Regarding efficacy, no complete remissions (CR) were reported. Out of 18 evaluable patients 5 (27.5%) were in partial remission (PR) in Part I at month 4 and 7 (63.6%) were in PR in part II at month 4. Rapid and profound lymphocyte depletion was observed and sustained in most subjects. No dose limiting toxicity was reported.

UTX-TGR-103

The doublet U2 which will be utilized in this protocol has been evaluated in a Phase I/Ib trial in CLL/SLL and NHL, initially reported by (Lunning et al ASH 2015). In the doublet cohort one dose limiting toxicity (DLT) of Grade 4 neutropenia occurred in CLL cohort which later resolved in later cycles. In this study the most common AEs of Grade 3 or higher occurring in more than 3% of patients were neutropenia (28%), diarrhea (8%), abdominal pain (8%), pneumonia (8%), thrombocytopenia (4%), asthenia (4%), febrile neutropenia (4%), sepsis (4%). Grade 3 or greater IRRs were experienced in only 1% of subjects.

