12.1.2 Umbralisib Risks

The following adverse events were observed in patients treated with single agent umbralisib and were considered at least possibly related to the study medication, umbralisib. The preliminary safety data as of May 1, 2018 is provided for a total of 136 subjects exposed to single agent

umbralisib with a maximum follow up of 5+ years. See the latest umbralisib investigator brochure for a complete list of all adverse events reported regardless of causality.

Very Common ($\geq 10\%$)

- **Blood and Lymphatic System Disorders:** neutropenia
- **Gastrointestinal Disorders:** nausea, diarrhea, vomiting
- **General Disorders and Administration Site Conditions:** fatigue

Common ($\geq 2\% - < 10\%$)

- **Blood and Lymphatic System Disorders:** anemia, thrombocytopenia, leukocytosis, lymphocytosis
- **Ear and Labyrinth Disorders:** tinnitus
- **Eye Disorders:** vision blurred
- **Gastrointestinal Disorders:** constipation, abdominal pain, abdominal distension, dyspepsia, colitis, dry mouth
- **General Disorders and Administration Site Conditions:** pyrexia, edema peripheral
- **Infections and Infestations:** pneumonia, oral candidiasis
- **Injury, Poisoning and Procedural Complications:** contusion
- **Investigations:** weight decreased, alanine aminotransferase increased, aspartate aminotransferase increased, blood creatinine increased
- **Metabolism and Nutrition Disorders:** decreased appetite, dehydration, hyperglycaemia, hypokalaemia, hypophosphataemia
- **Musculoskeletal and Connective Tissue Disorders:** muscle spasms, pain in extremity
- **Nervous System Disorders:** dizziness, headache, dysgeusia, tremor
- **Psychiatric Disorders:** insomnia
- **Respiratory, Thoracic and Mediastinal Disorders:** cough
- **Skin and Subcutaneous Tissue Disorders:** rash maculo-papular, alopecia, night sweats, pruritus, rash

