12.1.3 Ublituximab + Umbralisib Combination Risks

Adverse Events and Potential Risks

The following adverse events were observed in patients treated with the combination of ublituximab + umbralisib and were considered at least possibly related to one or both of the study medications. The preliminary safety data as of May 1, 2018 is provided for a total of 75 subjects exposed to ublituximab + umbralisib with a maximum follow up of 3+ years. See the latest ublituximab and umbralisib investigator brochures for a complete list of all adverse events reported regardless of causality.

Very Common ($\geq 10\%$)

- **Blood and Lymphatic System Disorders:** anemia, neutropenia
- **Gastrointestinal Disorders:** diarrhea, nausea, vomiting
- **General Disorders and Administration Site Conditions:** fatigue

- **Injury, Poisoning and Procedural Complications:** infusion related reaction
- **Metabolism and Nutrition Disorders:** decreased appetite

Common ($\geq 1\% - < 10\%$)

- **Blood and Lymphatic System Disorders:** thrombocytopenia
- **Cardiac Disorders:** cardiac failure congestive
- **Ear and Labyrinth Disorders:** ear congestion, ear discomfort
- **Eye Disorders:** conjunctival pallor, conjunctivitis, corneal edema, vision blurred
- **Gastrointestinal Disorders:** abdominal discomfort, abdominal distension, abdominal pain, constipation, dyspepsia, flatulence, gastroesophageal reflux disease, hematochezia, salivary hypersecretion, stomatitis
- **General Disorders and Administration Site Conditions:** asthenia, chills, face edema, infusion site pain, local swelling, edema peripheral, pyrexia, systemic inflammatory response syndrome
- **Hepatobiliary Disorders:** hyperbilirubinaemia
- **Immune System Disorders:** hypogammaglobulinaemia
- **Infections and Infestations:** bronchitis, cellulitis, clostridium difficile colitis, enterocolitis infectious, oral candidiasis, oral herpes, otitis media, pneumonia, pneumonia streptococcal, rhinovirus infection, sepsis, sepsis syndrome, sinusitis, skin infection, upper respiratory tract infection, urinary tract infection
- **Injury, Poisoning and Procedural Complications:** wound
- **Investigations:** alanine aminotransferase increased, aspartate aminotransferase increased, blood alkaline phosphatase increased, blood creatinine increased, computerized tomogram thorax abnormal, immunoglobulins decreased, weight decreased

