- **Metabolism and Nutrition Disorders:** dehydration, failure to thrive, hyperglycaemia, hyperuricaemia, hypokalaemia, hypophosphataemia
- **Musculoskeletal and Connective Tissue Disorders:** joint swelling, muscle spasms, muscular weakness, myalgia, pain in extremity
- **Nervous System Disorders:** dizziness, dysgeusia, headache, lethargy, sinus headache, somnolence
- **Psychiatric Disorders:** agitation, anxiety
- **Renal and Urinary Disorders:** micturition urgency, renal failure, renal failure acute
- **Reproductive System and Breast Disorders:** scrotal cyst, semen discoloration
- **Respiratory, Thoracic and Mediastinal Disorders:** choking, cough, dysphonia, dyspnea, epistaxis, hypoxia, oropharyngeal pain, pneumonitis, productive cough, sinus congestion
- **Skin and Subcutaneous Tissue Disorders:** alopecia, cold sweat, dermatitis acneiform, dermatitis bullous, dry skin, ecchymosis, pruritus, rash, maculo-papular, rosacea, urticaria
- **Vascular Disorders:** hypertension

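### Phosphate is not in the scheduled chemistry panel, although hypophosphataemia is listed as a common umbralisib-related event

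*Combined protocol and SAP*

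**What the plan says.** Table 1 in Section 5.1 schedules serum chemistry (CMP), and footnote a spells out its content: "CMP includes a Basic Metabolic panel (Sodium, potassium, chloride, bicarb, blood urea nitrogen, creatinine, calcium, glucose) and a Hepatic function panel", the hepatic part being "protein total, albumin, globulin, alanine aminotransferase, aspartate aminotransferase, total bilirubin, alkaline phosphatase". The one add-on is uric acid, at five early visits. The visit lists in Sections 5.1.1 to 5.1.2.8 and the follow-up list in Section 5.5 call for CMP (with uric acid at the early visits) and nowhere name phosphate.

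Section 12.1.2 gives events considered at least possibly related to single-agent umbralisib in 136 subjects. Its common band (2% to under 10%) includes this metabolic line: "decreased appetite, dehydration, hyperglycaemia, hypokalaemia, hypophosphataemia". Section 12.1.3 gives the combination list for 75 subjects, with events that "were considered at least possibly related to one or both of the study medications". Its common band (1% to under 10%) includes "dehydration, failure to thrive, hyperglycaemia, hyperuricaemia, hypokalaemia, hypophosphataemia".

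On use of the data, Section 1.2 states: "Secondary objectives to be evaluated in the study will be complete remission rate, duration of response, and safety". Section 12 names clinical laboratory tests as one source of safety information, Section 12.1 counts an abnormal laboratory finding as a possible adverse event, and Section 11.2.2 plans to report incidence by specific term for the whole cohort.

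**The concern.** The plan names a laboratory abnormality as drug-related, intends to tabulate adverse events term by term, and then does not schedule the test that would detect it. A site following the schedule exactly would never measure phosphate unless something prompted it. Two things follow. An asymptomatic fall in phosphate would usually go unseen, so the row for this term would tend to be too low. And because nothing is measured at screening, a low value found later on a prompted test could not be compared with the subject's level before umbralisib. Umbralisib is taken daily until progression or toxicity (Section 5.2), so the gap lasts throughout treatment. What is at stake is the completeness of one row in a descriptive safety table, not the primary endpoint.

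**Working it through.** The plan states no figure on this point, so there is nothing to reproduce. The check is a count, a matching of terms to tests, and some arithmetic for scale.

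**1. Chemistry visits (Table 1, CMP row).** Screening 1; Cycle -1 Days 1 and 15, 2; Cycle 1 Days 1, 2, 8 and 15, 4; Cycles 2 to 6 Day 1, 5; C7, C10, C13, C16, C19, C22 and C25 Day 1, 7. Total 1 + 2 + 4 + 5 + 7 = 19 through C25D1. The end-of-treatment and follow-up columns make 21 marked columns, and the C25D1 and follow-up columns then repeat every 3 months. Phosphate is scheduled at 0 of 19 (and 0 of 21); potassium and glucose at all of them.

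**2. Laboratory-defined terms on the umbralisib-alone list (Section 12.1.2) against scheduled tests.**

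| Term | Scheduled test |
|---|---|
| Neutropenia, anemia, thrombocytopenia, leukocytosis, lymphocytosis | CBC with differential |
| ALT, AST and creatinine increased | CMP |
| Hyperglycaemia, hypokalaemia | CMP |
| Hypophosphataemia | none |

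That is 5 + 3 + 2 = 10 of 11 terms covered, and hypophosphataemia is the exception.

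**3. The other two lists.** Gamma-glutamyltransferase increased is on the ublituximab list (Section 12.1.1) but is not in the hepatic panel. Hypogammaglobulinaemia and decreased immunoglobulins are on the combination list (Section 12.1.3), and no immunoglobulin assay is scheduled. Hyperuricaemia, also on the combination list, does have a scheduled test at five visits.

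**4. Expected occurrences in 24 subjects, if the listed rates apply here.**
- Combination band: 24 × 0.01 = 0.24 to 24 × 0.10 = 2.4.
- Read as 1 to 7 of the 75 source subjects: 24 × 1/75 = 0.32 to 24 × 7/75 = 2.24.
- Umbralisib-alone band: 24 × 0.02 = 0.48 to 2.4. The chance of at least one case, 1 − (1 − p)^24, is 38% at p = 2%, 71% at 5% and 92% just under 10%.

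These are cases expected to occur, not cases missed. The number missed depends on what share is silent and how often phosphate is ordered anyway, and the documents give neither.

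**5. What a zero row would mean.** The exact two-sided 95% upper limit for 0 of 24 is 1 − 0.025^(1/24) = 14.2%. Zero recorded cases would not exclude the listed band, with or without scheduled testing.

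**6. Grade 3 or higher.** Section 2.4.5 lists the Grade 3 or higher events seen in more than 3% of patients in the earlier combination study, and hypophosphataemia is not among them. That is an observed rate of 3% or less. At a true rate of 3%, 24 × 0.03 = 0.72 subjects would be expected, with a chance of at least one of 1 − 0.97^24 = 52%. These are not maxima. If the denominator was the 75 subjects mentioned in the same section (an assumption), 2 of 75 has an exact 95% upper limit of 9.3%, and 24 × 0.093 = 2.2. How phosphate was monitored in that study is not stated.

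**7. Cost.** 19 × 24 = 456 assays through C25D1 if every subject gets that far.

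**The case against.** The best case against acting is that this is a preference about panel content in a 24-subject descriptive pilot. Investigators may order phosphate when there is reason to, adverse events are collected at every timepoint, and electrolyte replacement is already permitted (Section 5.3). The combination band starts at 1% of 75 subjects, so the listing there could rest on a single case. All of this is fair and limits the point to a minor one. It does not supply a baseline or a routine look for silent cases. Nor does it help to read the panel description as open-ended: the analytes are itemised, and even uric acid had to be written in separately.

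Four stronger readings are tempting, and the documents do not support them.

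- A reader might infer that phosphate is the only unscheduled laboratory term in the protocol. That holds for the umbralisib-alone list only; gamma-glutamyltransferase and immunoglobulins are gaps on the other lists.
- A reader might infer that the tabulated incidence can only be too low. Without a baseline, a low value that predates treatment could be recorded as an on-treatment event, which pushes the other way. Under-recording of silent cases is the likelier effect, not a certainty.
- A reader might infer that potassium and glucose events are completely captured by contrast. From Cycle 7 visits are three 28-day cycles apart, about 12 weeks, so transient changes in those are missed too.
- A reader might infer from Section 2.4.5 that Grade 3 or higher cases are capped at 3%. Absence from a list of observed rates sets no ceiling on the true rate.

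**Conclusion.** The point stands as a minor gap in safety ascertainment. A term that the protocol itself attributes to umbralisib and to the combination has no scheduled test at any of the 19 chemistry visits through C25D1, nor at end of treatment or follow-up. Silent cases are likely to be under-recorded, and prompted low values have no baseline. The overall response rate is unaffected. The scale rests on the assumption that the listed frequencies carry over to this population; on that basis a few cases at most would be expected among 24 subjects, and how many would go unrecorded cannot be worked out. The documents do not show that any safety conclusion would change.

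**What to change.** In Table 1 footnote a, add phosphate to the Basic Metabolic panel analytes, for example after calcium. It then runs wherever CMP is marked, including screening, which supplies the baseline. The visit lists refer to CMP as a whole and need no edit.

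The cost is one assay on blood already drawn: about 456 for 24 subjects through C25D1, plus those at later, end-of-treatment and follow-up visits. No new scheduled visit, procedure or staff is needed.

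The downside is a few more laboratory adverse events and an occasional Grade 3 or higher value that triggers the existing Table 4 hold for other non-hematological events, under which ublituximab restarts only after 7 days of resumed umbralisib. Leave Table 4 as it is. An exception for one electrolyte would relax a safety rule without a reason that also separates phosphate from potassium or glucose, and Section 5.3 already allows replacement.

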5.1.1 Screening Visit

- Informed consent
- Inclusion/exclusion checklist
- ECOG
- Medical history
- Physical exam
- Vital Signs
- Height
- Weight
- EKG
- Bone marrow biopsy
- Bone marrow aspirate
- CBC with differential
- CMP (with uric acid)
- HIV
- Hepatitis antibody screen
- CMV testing by PCR
- For women of childbearing age serum B-HCG within 3 days prior to Cycle -1 Day 1
- CT neck, chest, abdomen and pelvis with contrast

5.1.2 Treatment Phase

5.1.2.1 Cycle -1 Day 1

- ECOG
- Medical history
- Physical exam
- Vital Signs
- Weight
- CBC with differential
- CMP (with uric acid)
- Research tubes (2 purple top tubes for banking)
- Umbralisib pill dispensation
- Adverse event assessment

5.1.2.2 Cycle -1 Day 15

- ECOG
- Medical history
- Physical exam
- Vital Signs
- Weight
- CBC with differential
- CMP (with uric acid)

- Umbralisib pill dispensation
- Adverse event assessment

5.1.2.3 Cycle 1 Day 1

- ECOG
- Medical history
- Physical exam
- Vital Signs
- Weight
- CBC with differential
- CMP (with uric acid)
- Research tubes (2 purple top tubes for banking)
- Ublituximab infusion
- Umbralisib pill dispensation
- Adverse event assessment

5.1.2.4 Cycle 1 Day 2

- Medical history
- Physical exam
- Vital Signs
- Weight
- CBC with differential
- CMP (with uric acid)
- Ublituximab infusion
- Adverse event assessment

5.1.2.5 Cycle 1 Day 8 and 15 (+/- 2 days)

- ECOG
- Medical history
- Vital Signs
- Weight
- CBC with differential
- CMP
- Ublituximab infusion
- Adverse event assessment

5.1.2.6 Cycle 2-6, Day 1 (+/- 2 days)

- ECOG
- Medical history
- Physical exam

- Vital Signs
- Weight
- CBC with differential
- CMP
- Research tubes (2 purple top tubes for banking) (Cycle 2 only)
- Ublituximab infusion (+/- 3 days)
- Umbralisib pill dispensation
- CT neck, chest, abdomen and pelvis with contrast (Prior to C2D1 only +/- 7 days)
- CMV testing by PCR
- Adverse event assessment

5.1.2.7 Cycle 7, Day 1 and Beyond, Study visits occur every 3 cycles with a Day 1 visit (+/- 5 days)

- ECOG
- Medical history
- Physical exam
- Vital Signs
- Weight
- CBC with differential
- CMP
- Research tubes (2 purple top tubes for banking) (Cycle 7, 13, 19, 25 only)
- Umbralisib pill dispensation
- CT neck, chest, abdomen and pelvis with contrast (Prior to C7D1, C13D1, C19D1, C25D1 only +/- 7 days)
- CT neck, chest, abdomen and pelvis C37D1, C49D1, C61D1 +/- 7 days for subjects on study beyond 2 years.
- CMV testing by PCR
- Adverse event assessment
- After Cycle 7D1 study visit and response assessments subjects must be evaluated for objective response by treating investigator. See Section 5.4.1 for further details in subject management.

